10.4.2 Contraception Guidance

CONTRACEPTIVES^a ALLOWED DURING THE STUDY INCLUDE:

Highly Effective Methods^b **That Have Low User Dependency** *Failure rate of* < 1% *per year when used consistently and correctly.*

- Implantable progestogen-only hormone contraception associated with inhibition of ovulation^c
- Intrauterine device (IUD)
- Intrauterine hormone-releasing system (IUS)^c
- Bilateral tubal occlusion
- Azoospermic partner (vasectomized or due to a medical cause)

Azoospermia is a highly effective contraceptive method provided that the partner is the sole sexual partner of the woman of childbearing potential and the absence of sperm has been confirmed. If not, an additional highly effective method of contraception should be used. Spermatogenesis cycle is approximately 90 days. Note: documentation of azoospermia for a male participant can come from the site personnel's review of the participant's medical records, medical examination, or medical history interview.

Sexual abstinence

Sexual abstinence is considered a highly effective method only if defined as refraining from heterosexual intercourse during the entire period of risk associated with the study intervention. The reliability of sexual abstinence needs to be evaluated in relation to the duration of the study and the preferred and usual lifestyle of the participant.

- a) Contraceptive use by men or women should be consistent with local regulations regarding the use of contraceptive methods for those participating in clinical studies.
- b) Failure rate of < 1% per year when used consistently and correctly. Typical use failure rates differ from those when used consistently and correctly.
- c) If locally required, in accordance with Clinical Trial Facilitation Group (CTFG) guidelines, acceptable contraceptive methods are limited to those which inhibit ovulation as the primary mode of action.

Note: Periodic abstinence (calendar, symptothermal, postovulation methods), withdrawal (coitus interruptus), spermicides only, and lactational amenorrhea method (LAM) are not acceptable methods of contraception for this study. Male condom and female condom should not be used together (due to risk of failure from friction).

29 NOV 2023 Page: 43 of 44

11. References

## **Version History**

This Statistical Analysis Plan (SAP) for Study 21683 is based on the protocol Version 1.0 dated 29 NOV 2023.

SAP Version	Date	Change	Rationale
1.0		Not applicable	Original version

#### List of Abbreviations

AE adverse event

AESI adverse event of special interest

ARNI angiotensin receptor-neprilysin inhibitor

ATC Anatomical Therapeutic Chemical

cGMP cyclic guanosine monophosphate

CSP Clinical Study Protocol

CV cardiovascular

DBP diastolic blood pressure

ECG electrocardiogram

eCRF electronic Case Report Form

EF ejection fraction

eGFR estimated glomerular filtration rate

EMA European Medicines Agency

EU European Union

FDA Food and Drug Administration

GDMT guideline-directed medical therapy for heart failure

hCG human chorionic gonadotropin

HF heart failure

HFrEF heart failure with reduced ejection fraction

IRT interactive response technology

LLOQ lower limit of quantification

#### Statistical Analysis Plan BAY 1021189 / 21683

Version 1.0 Page: 5 of 15

NO nitric oxide

PT preferred term

SAF safety analysis set

SAP Statistical Analysis Plan

SBP systolic blood pressure

sGC soluble guanylate cyclase

SGLT2i sodium-glucose cotransporter 2 inhibitor

SOC system organ class

TEAE treatment-emergent adverse event

ULN upper limit of normal

ULOQ upper limit of quantification

VICTORIA VerICiguaT GlObal Study in Subjects With Heart Failure With Reduced EjectIon FrAction

Version 1.0 Page: 6 of 15

#### 1. Introduction

Chronic HFrEF is a major source of morbidity and mortality. Clinical outcomes for patients with chronic HFrEF remain poor, despite contemporary evidence-based therapies. Therefore, drugs are needed that effectively target disease mechanisms not addressed by current standard therapy.

Vericiguat, a novel soluble sGC stimulator, is approved for the treatment of HFrEF. Decreased NO availability, sGC desensitization to NO, sGC deficiency, and cGMP signaling are potential contributing factors for HF disease progression. Vericiguat works via stimulation of sGC in the critical NO-sGC-cGMP pathway. Vericiguat has a novel mode of action that targets endothelial dysfunction to improve regulation of vascular tone and myocardial function. Pharmacokinetic, pharmacodynamic, safety and efficacy profiles of vericiguat have been well characterized in a series of Phase 1 (29 studies), Phase 2 (3 studies) and Phase 3 (1 study) studies. In the global Phase 3 study, VICTORIA, treatment of 5050 patients with chronic heart failure with reduced ejection fraction with vericiguat on top of the standard of care resulted in a 10% reduction in the primary outcome of a composite of death from cardiovascular causes or first hospitalization for HF after a median treatment period of 10.8 months (Armstrong et al. 2020).

In VICTORIA, vericiguat was generally safe and well tolerated with low incidence of symptomatic hypotension and syncope, using a titration regimen (a starting dose of 2.5 mg followed by a 2-step up-titration to the target 10 mg dose) guided by symptoms and SBP to mitigate the risk of hypotension. Correlation between vericiguat plasma concentrations and hemodynamic parameters such as heart rate and SBP has been observed following first dose administration but dissipated with repeated dosing. In addition, no meaningful exposure-response relationship was observed for the incidence of symptomatic hypotension or syncope – after first dose and further during the study. This led to the implementation of a symptom-and SBP-guided 2-step titration scheme for vericiguat posology.

In clinical practice, titration of HF medications, including vericiguat, is often compromised by limited follow-up opportunities and complexity of care at each follow-up visit. This results in under treatment of HFrEF patients due to failure to achieve the maximum efficacious dose for treatments with established benefit. Achieving the target dose of HF treatments in a safe and fast manner remains a large unmet medical need in HFrEF patients. Keeping drug initiation/titration regimens as simple and as safe as possible is critical to HFrEF patients in order to achieve optimal doses of GDMT.

Currently, initiation of vericiguat starts with 2.5 mg, increasing to 5 mg at 2 weeks, then 10 mg at 4 weeks. Removing the 2.5 mg step has the benefit of patients starting on a more efficacious dose and achieving maximal (target) dose with a single titration.

This SAP is based on the clinical study protocol version 1.0 (dated 29 NOV 2023). The SAP describes the final analysis of the study. No statistical interim analysis will be performed. Table, figure and listing specifications are contained in a separate document. There are no changes to the analyses described in the protocol.

Version 1.0 Page: 7 of 15

#### 1.1 Objectives and Endpoints

Objectives	Endpoints
Primary	•
To evaluate the tolerability of 5 mg as a starting dose of vericiguat	Treatment tolerability, defined as the completion of the two-week 5 mg dose without discontinuation of study intervention and without moderate to severe symptomatic hypotension between Visit 1 and Visit 2.
Secondary	

 
To describe safety events of initiation of 5 mg dose
 
To further evaluate the tolerability of 5 mg as a starting dose of vericiguat
 
	
 
Any AE reported between Visit 1 and Visit 2.
 
Absence of AE related to study intervention between Visit 1 and Visit 2.
 
Continuous intake of study intervention between Visit 1 and Visit 2 or restart of study intervention after any temporary interruption.
 

[figure not shown]
## 1.2 Study Design.

This is a single arm, open label study of vericiguat initiation at 5 mg in HFrEF patients with EF <45%. The total study duration is approximately 4 weeks, including a 2-week screening period and a 2-week treatment period.

Unscheduled visits may be utilized between Visits 1 and 2 at the discretion of the investigator for AE review and reporting.

The intention of the study is to maintain participants on the 5 mg dose of study intervention for the 2-week treatment period. Dose modifications are not planned within the scheme of this study. Temporary interruption of study intervention is permitted at any time during the study at the investigator's discretion.

Figure 1-1: Schema

A = assignment to study intervention, D = day, EoS = end of study, S= screening, V = visit

This is an open label study. No interim analysis is planned.

Due to the nature of this study, participant-level treatment assignment information is available during study conduct. However, manual interim calculations of tolerability rates will not be done in order to protect the integrity of the study. Any analysis of study data, including the analysis of the primary endpoint, will be performed after database release.

Version 1.0 Page: 8 of 15

Approximately 120 participants will be screened to achieve at least 100 participants who are assigned to study intervention and complete the treatment period of up to 2 weeks.

The study will enroll participants with chronic heart failure with ejection fraction <45%, with and without recent worsening HF. Enrollment caps will be applied to ensure enrollment of the desired proportion of participants with (group 1) and without (group 2) recent HF event (approximately 50% in each group). These two groups will also reflect contemporary standards of care in HF, with a goal of enrolling at least 30% of participants receiving an ARNI and 30% a SGLT2 inhibitor. The desired proportion of participants on GDMT may be achieved by capping the number of participants not on ARNI or SGLT2i therapy. These enrollment caps will be managed in the IRT.

Prospective approval of protocol deviations to recruitment and enrollment criteria, also known as protocol waivers or exemptions, is not permitted.

## 2. Statistical Hypotheses

The analyses presented here will be descriptive in nature and thus no statistical hypothesis tests will be performed.

## 2.1 Multiplicity Adjustment

There will be no multiplicity adjustment performed as it is not applicable to this study.

# 3. Analysis Sets

For the purposes of analysis, the following analysis set is defined:

Participant Analysis Set	Description	
Safety analysis set (SAF)	All participants assigned to investigational intervention who were exposed to study intervention at least once.	

Final decisions regarding the assignment of participants to analysis sets will be made during the review of study data and documented in the final list of important deviations, validity findings and assignment to the analysis sets.

## 4. Statistical Analyses

#### 4.1 General Considerations

The statistical evaluation will be performed by using the software SAS (release 9.4 or higher; SAS Institute Inc., Cary, NC, USA).

All analyses will be performed on the SAF.

In general, continuous data will be summarized using the number of participants, mean, standard deviation, minimum, median, and maximum. For categorical data frequency tables will be provided. Summary statistics and frequency tables will be presented for Vericiguat, i.e. overall, and by visit (if applicable).

All data will be presented in the participant data listing as they are recorded on the eCRF, i.e., partially missing data will appear as such. Imputation of missing data is not planned.

Listings will be provided sorted by participant identifier.

Version 1.0 Page: 9 of 15

Data from unscheduled measurements will be listed, but not included in summary statistics or frequency tables.

#### 4.1.1 Baseline

Regarding vital signs the baseline assessment will be the assessment at Day 1 (Visit 1). If the assessment on Day 1 (Visit 1) is missing, then baseline will be the last available assessment before first study drug intake (i.e. usually the screening assessment).

Other parameters, such as ECG and laboratory data, will only be assessed once, therefore no baseline is defined.

## 4.1.2 Repeated Measurements

If more than one measurement is available at screening, the last observation of those will be used for descriptive statistics tables as well as for frequency tables. In case of multiple measurements at planned time points after intake of study intervention, the earliest measured value will be used for descriptive statistics tables as well as for frequency tables.

## 4.1.3 Laboratory Values outside the calibration range

For the calculation of descriptive statistics, a data point present in the database as '<x' or '>x' will be substituted by x itself. In tables showing mean values, where such values are included in the calculation of mean values, these means will be marked. Corresponding tables will get a footnote indicating this. Tables displaying minimum and maximum values will present "<x" and ">x" as minimum and maximum, respectively.

#### 4.2 Primary Endpoint Analysis

#### 4.2.1 Definition of Endpoints

The primary endpoint of tolerability is defined as the completion of the two-week 5 mg dose without discontinuation of study intervention and without symptomatic hypotension of moderate to severe intensity between Visit 1 and Visit 2. Participants with discontinuation of study intervention or symptomatic hypotension of moderate to severe intensity would not meet criteria for the primary endpoint of treatment tolerability. Discontinuation is defined as the inability to complete treatment between Visit 1 and Visit 2 where one missing/forgotten dose is permitted.

#### 4.2.2 Main Analytical Approach

To assess the primary objective the proportion of participants reaching tolerability as defined in Section 4.2.1 will be calculated.

The proportion will be derived by dividing the number of participants reaching tolerability by all participants included in the SAF. Thus, in the case of 100 participants included in the SAF, all 100 will be included as part of the denominator and the numerator will only include the number of participants who completed the two-week 5 mg dose without any study intervention discontinuation (where one missing/ forgotten dose is permitted) and without symptomatic hypotension of moderate to severe intensity. See also Table 4-1. The absolute number of participants reaching tolerability will be provided in addition.

Version 1.0 Page: 10 of 15

# 4.2.3 Sensitivity Analyses

Table 4-1 describes the different proportions of participants included in the primary, secondary and sensitivity tolerability analysis. While the denominator will, for all cases, contain all participants included in the SAF, the numerator will contain the following listed subgroups of participants.

Table 4-1 Proportions for primary and primary sensitivity tolerability analyses

Analysis	Participants included in numerator	Explanation
Primary	Participants who completed the two-week treatment with maximum one day interruption and without symptomatic hypotension of moderate to severe intensity between Visit 1 and Visit 2.	Tolerability assessment as defined in the CSP.
Sensitivity	Participants who completed the two-week treatment with maximum two days interruption and without symptomatic hypotension of moderate to severe intensity between Visit 1 and Visit 2.	More generous compared to primary considering that a second day with interruption, independent from reason of interruption, might still indicate tolerability of intervention.

# 4.2.4 Supplementary Analysis/Analyses

There will be no supplementary analyses.

## 4.3 Secondary Endpoints Analysis

#### 4.3.1 Definition of Endpoints

The secondary endpoints are defined as follows:

- Any AE reported between Visit 1 and Visit 2.
- Absence of AEs related to study intervention between Visit 1 and Visit 2.
- Continuous intake of study intervention between Visit 1 and Visit 2 or restart of study intervention after any temporary interruption.

#### 4.3.2 Main Analytical Approach

#### 4.3.2.1 Analyses of adverse events

For a detailed description of the AE analysis please refer to Section 4.5.2.

#### 4.3.2.2 Secondary tolerability analyses

To assess the secondary objective regarding tolerability, the proportion of participants as described in Table 4-2 will be calculated.

Version 1.0 Page: 11 of 15

Table 4-2 Proportions for secondary tolerability analyses

Analysis	Participants included in numerator	Explanation
Secondary 1 (tolerability)	Participants who did not have an AE related to study intervention between Visit 1 and Visit 2.	As defined in the CSP. Tolerability in the sense of looking at AEs; independent from compliance, as lack of compliance could have different reasons.
Secondary 2 (tolerability)	Participants who completed the two-week treatment with continuous intervention intake or were able to restart intervention after temporary interruption.	As defined in the CSP. Restart of intervention even after interruptions due to AEs is allowed.

The proportions will be derived by dividing the number of participants reaching tolerability by all participants included in the SAF.

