7.3 Lost to Follow Up

A participant will be considered lost to follow-up if the participant fails to return for Visit 2 and is unable to be contacted by the study site.

The following actions must be taken if a participant fails to return to the clinic for a required study visit:

29 NOV 2023 Page: 25 of 44

- The site must attempt to contact the participant and reschedule the missed visit as soon as possible, counsel the participant on the importance of maintaining the assigned visit schedule, and ascertain whether the participant wishes to and/or should continue in the study.
- Before a participant is deemed lost to follow up, the investigator or designee must
 make every effort to regain contact with the participant (where possible, 3 telephone
 calls, and if necessary, a certified letter to the participant's last known mailing address
 or local equivalent methods). These contact attempts should be documented in the
 participant's medical record.
- Should the participant continue to be unreachable, the participant will be considered lost to follow up.

8. Study Assessments and Procedures

- Study procedures and their timing are summarized in the SoA. Protocol waivers or exemptions are not allowed.
- Adherence to the study design requirements, including those specified in the SoA, is essential and required for study conduct.
- All screening evaluations must be completed and reviewed to confirm that potential participants meet all eligibility criteria. The investigator will maintain a screening log to record details of all participants screened and to confirm eligibility or record reasons for screening failure, as applicable.
- Procedures conducted as part of the participant's routine clinical management (e.g., local laboratory) and obtained before signing of the ICF may be utilized for screening or baseline purposes provided the procedures met the protocol-specified criteria and were performed within the timeframe defined in the SoA.
- In the event of a significant study-continuity issue (e.g. caused by a pandemic), alternate strategies for participant visits, assessments, medication distribution and monitoring may be implemented by the sponsor or the investigator, as per local health authority/ethics requirements.

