9.3.2.2 Main Analytical Approach

Participants who meet the criteria for tolerability as defined in Section 9.3.2.1 will be considered for the numerator in the proportion of participants reaching tolerability. The denominator will contain all participants who were included in the SAF. Thus in the case of 100 participants included in the SAF, all 100 will be included as part of the denominator and the numerator will only include the number of participants who completed the two week 5 mg dose without any study intervention discontinuation and without symptomatic hypotension of moderate to severe intensity. There will be no imputation of missing data. A similar approach will be taken for the derivation of the proportion for the secondary endpoint analyses.

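### As worded, Secondary 1 scores participants with no AE assessment after Day 1 as free of related AEs; the SAP should require a documented assessment

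*SAP*

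**What the plan says.** - **Numerator** (SAP 4.3.2.2, Table 4-2, Secondary 1): "Participants who did not have an AE related to study intervention between Visit 1 and Visit 2". The table's explanation describes the endpoint as "independent from compliance, as lack of compliance could have different reasons".
- **Denominator** (same section): "The proportions will be derived by dividing the number of participants reaching tolerability by all participants included in the SAF". The SAF (SAP section 3) is "All participants assigned to investigational intervention who were exposed to study intervention at least once".
- **Missing data:** "There will be no imputation of missing data" (protocol 9.3.2.2) and "Imputation of missing data is not planned" (SAP 4.1). Protocol 9.3.2.2 adds: "A similar approach will be taken for the derivation of the proportion for the secondary endpoint analyses".
- **When AEs are reviewed** (protocol 1.3): at Visit 1 before dosing and two hours after, at Visit 2, and at any unscheduled visit.
- **Withdrawal and loss:** on withdrawal from the study an unscheduled visit is held if possible (protocol 7.2). A participant is "lost to follow-up if the participant fails to return for Visit 2" and, in addition, cannot be reached by the site (protocol 7.3). Participants who stop drug are to stay in the study until Visit 2 (protocol 7.1).
- **Primary numerator** (SAP 4.2.3, Table 4-1): requires completion of the two-week treatment with at most one day missed, and no moderate or severe symptomatic hypotension.
- **Further analyses of the secondary endpoints:** none (SAP 4.3.3 and 4.3.4).

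**The concern.** Secondary 1 is met by the absence of a record. Nothing in its definition asks whether anyone looked for an AE after Day 1. A participant who takes the first dose, leaves after the two-hour check and is never seen or reached again has no related AE on file, belongs to the SAF, and so satisfies the numerator. The definition refers to a window that closes at Visit 2, and for this participant Visit 2 never took place.

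The row is labelled a tolerability proportion, and under this wording unknown status can only raise it. The SAP is more cautious elsewhere: SAP 4.5.2 treats an AE with missing relationship as related and one with missing intensity as severe. Those rules need a reported event to act on, so they do not reach a participant who was never assessed. The primary works the other way, because its numerator asks for something positive, namely completed treatment.

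At stake is the reading of one descriptive secondary figure, and whether its scoring rule is fixed before data are seen in an open-label study.

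**Working it through.** No figure in the plan bears on this, so there is nothing to reproduce. The approximate sample size of 100 has no formula behind it (SAP section 5), and neither document gives a loss-to-follow-up rate or a related-AE rate. Two figures come near but cannot serve. The step from 120 screened to 100 completing mixes screen failure with loss (20/120 = 16.7% combined). The 96.1% of VICTORIA participants on vericiguat who remained on treatment without interruption to day 14 (protocol 2.2) concerns drug intake at a 2.5 mg start, not contact with the site.

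**Inputs.** SAF = 100, the documents' own example (protocol 9.3.2.2; SAP 4.2.2). A = participants with a recorded related AE, taken as about 10% of those assessed (assumption). L = participants with no AE assessment after Day 1 and no related AE on record (assumption, 2 to 10). q = the true related-AE rate among those L (assumption, 10% to 30%).

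**Step 1: three ways to score.**
- As worded: (100 − A)/100
- Unassessed scored as not meeting the endpoint: (100 − A − L)/100
- Assessed participants only: (100 − L − A)/(100 − L)

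| A | L | As worded | Unassessed not meeting | Assessed only |
|---|---|---|---|---|
| 10 | 2 | 90/100 = 90.0% | 88/100 = 88.0% | 88/98 = 89.8% |
| 10 | 4 | 90/100 = 90.0% | 86/100 = 86.0% | 86/96 = 89.6% |
| 10 | 5 | 90/100 = 90.0% | 85/100 = 85.0% | 85/95 = 89.5% |
| 9 | 10 | 91/100 = 91.0% | 81/100 = 81.0% | 81/90 = 90.0% |

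The first two columns differ by exactly L points. They are the upper and lower limits of the proportion that full assessment would have given.

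**Step 2: expected overstatement.** With full assessment, the expected number free of related AEs is 100 − A − q × L. The wording gives 100 − A. The difference is q × L points:
- q = 10%, L = 2: 0.10 × 2 = 0.2 points
- q = 20%, L = 5: 0.20 × 5 = 1.0 point
- q = 30%, L = 10: 0.30 × 10 = 3.0 points

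The full L points arise only if q = 100%. For scale, the exact 95% interval around 90/100 is 82.4% to 95.1%.

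**Step 3: against the primary.** Suppose there are no AEs at all and the L participants fall outside the primary numerator. The primary is then (100 − L)/100 and Secondary 1 as worded is 100/100: 95% against 100% at L = 5.

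**The case against.** The strongest reply is that the plan nowhere says unassessed participants count as free of AEs. The protocol carries the primary's approach over to the secondary proportions and rules out imputation, which could be taken to require confirmed absence. That reading is possible, but no sentence states it, and a programmer following Table 4-2 would count everyone without a related-AE record.

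The SAP also means this endpoint to be separate from compliance. That stands for participants who stop or miss drug: they are to be seen at Visit 2, their AE status is then known, and counting them as free of related AEs when none is found is intended. It does not settle what to do when status is unknown.

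Four stronger readings are tempting, and the documents do not support them.
- **Everyone who withdraws or misses Visit 2 is affected.** Loss to follow-up also requires that the participant cannot be reached. Sites are to make repeated contact attempts, and withdrawal calls for an exit visit where possible. A related AE recorded before leaving already counts against the endpoint.
- **The gap of L points is the bias.** It is the ceiling; the assessed-only figures lie within about 1 point of the as-worded ones.
- **Early leavers tolerated the drug worse.** This is plausible, but neither document offers evidence for it.
- **The primary certainly scores lost participants as failures.** This follows from the completion requirement, but protocol 6.5 deems unreturned tablets taken unless otherwise specified, so a lost participant with an unreturned bottle could be recorded as fully dosed.

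It is also fair to say that scoring the unassessed as failures is itself an assumption, which is why both figures should be shown. The disposition summary (SAP 6.1.1) lets a reader bound the effect roughly, but it does not give the number without an AE assessment.

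**Conclusion.** The point holds on the wording and is minor. Table 4-2 gives a favourable score to participants whose AE status is unknown for nearly the whole window, and no planned analysis shows the effect. The error can run only towards better tolerability, but the group is narrow: no Visit 2, no exit or unscheduled visit, no other contact after the Day 1 check, and no related AE already recorded. At SAF = 100 the overstatement is at most 1 point per such participant and is expected to be q × L points; L and q are assumptions throughout. Over two weeks L may well be small or zero, in which case no figure changes. The endpoint is secondary and descriptive, with no test and no decision threshold.

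**What to change.** In SAP 4.3.2.2:

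1. Count a participant as meeting Secondary 1 only if an AE assessment is documented at Visit 2, or at a later or study-exit contact, and no related AE was recorded in the window. Someone seen once mid-window and then lost would count as lacking that assessment.
2. Print the number of SAF participants without such an assessment beside the proportion.
3. Show the proportion twice: with those participants scored as not meeting the endpoint, and as currently worded. The two figures bound the result.
4. State that the protocol 6.5 rule on unreturned tablets does not by itself establish completed treatment for a participant lost to follow-up. This settles the primary's scoring as well.

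The cost is SAP wording and one extra table row, with no new data collection. The downside is a slightly less favourable figure if anyone is lost.
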